Study Design: The prevalence of ACS will be ascertained with a cross-sectional survey of a representative sample of all casualty department patients presenting with chest pain or shortness of breath. The prevalence of acute myocardial infarction will be determined by obtaining electrocardiograms (ECGs) and point-of-care troponins on all patients presenting with symptoms suggestive of ACS. Quantitative data concerning ACS knowledge and barriers will be obtained by patient knowledge, attitude, and practice (KAP) surveys. Qualitative information regarding barriers to care, healthcare seeking behaviors, and management of ACS will be obtained using patient focus groups and in-depth interviews with ED providers.

Study Population: All participants will be >17 years of age and be able to speak Swahili (patients or families) or English (healthcare practitioners). We will exclude patients with an inability to respond to the survey due to the severity of their illness or injury. We plan to enroll 500 patients in the observational study of patients with ACS-related symptoms and 500 patients in the ACS prevalence study.

Inclusion/ Exclusion Criteria:

Patients will be included in the prospective observational study of ACS-related symptoms and prevalence of myocardial infarction study if they have a primary or secondary chief complaint of chest pain or shortness of breath. All patients must be >17 years of age, be seeking care at KCMC in the casualty department, be clinically sober at the time of enrollment, be able to communicate in Swahili or English and consent to participate. Patients will be excluded from enrollment if they are medically unstable or have a deteriorating condition, are too critically ill to participate, are <18 years of age.

Sample Size Calculation:

Reported prevalence of myocardial ischemia among various African sub-populations (not general ED populations presenting with chest pain) range from 0.2%⁹ to 10.4%¹⁰. Assuming the prevalence of ischemic ECGs among ED patients with chest pain will be at the high end of this range (10%), then 210 patients will need to be enrolled in order to report this prevalence with a precision of +/- 5%.

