The proportion of ED patients with chest pain in Tanzania is unknown, but in developed settings is typically around 10%.^{11, 12} Assuming a similar proportion of patients will be eligible for inclusion in our study, and given current patient volumes at KCMC (25 adults/dayshift), enrollment will need to be conducted for 5 months to achieve the desired sample size.

Instruments/Procedures:

KAP (Specific Objective 1): A focused knowledge, attitude, and practice survey (KAP) survey will be developed, adapting questions from existing cardiovascular KAP surveys used elsewhere¹³⁻¹⁶. The survey will piloted on a small sample (N<20) of persons (who will be excluded from the final study) in order to report upon the internal consistency or reliability of the survey in Kiswahili and to assess the content validity of the survey in Kiswahili. It will be necessary to audio record the pilot interview sessions in order to allow for complete translation into English. Participants will not be identified by name on the tapes, and all recordings will be discarded after translation. This pilot will occur before the start of the study recruitment. After acceptability is assured the survey will then be given to all patients enrolled in the study.

Focus Group Methodology (Specific Objective 1): Focus groups will be held in Swahili with patients to better assess their understanding of chest pain and acute coronary syndrome, adherence with treatment, and any cultural barriers or culturally relevant solutions for a successful intervention and follow-up plan. Community members from randomly selected communities in Moshi Urban or Moshi Rural will participate in the focus groups. All patients who agree will be included until 3-4 focus groups are complete with a minimum of 10 participants each. Patients will be offered transportation money if they elect to return for focus groups. The focus groups will occur in a small quiet room near to the Casualty Department or in the local community.

In-depth Interview Methodology (Specific Objective 1): Approximately twenty in-depth interviews with a semi-structured format will be conducted in English or Swahili with casualty department physicians to assess their current practice surrounding the management of ACS in the emergency department. Implied consent language will be utilized. These conversations will be recorded and transcribed.

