these studies will be shared with the clinical team. The ECGs will be reviewed by two separate physicians, trained in either emergency medicine or cardiology to determine whether or not the ECG meets STEMI criteria. If there is a disagreement, a third physician will serve as the tiebreaker.

Survey Data Collection: Data will be collected on tablets and stored in a secure database by a trained data entry technician. Surveys for all components of this study will be verbally administered to patients and families due to variable literacy rates. They will be administered by healthcare providers in the standard medical language of English or Swahili. Results of urine dipstick will be recorded for the presence or absence of proteinuria. Results of troponins will be recorded and digital images of ECGs will be uploaded. Phone number of the patient and will be recorded in the log and de identified. No PHI will be entered into Redcap or any study database. The log will remain in a secure, locked cabinet the research office.

Focus Group Data Collection: Participants will take part in an informed consent process approved by the Duke and Tanzanian ethics committees before joining the focus group that is included in the survey consent form. Focus groups will be formed once 5-10 eligible interested participants are identified. Focus groups, led by trained research nurses or other trained research personnel, will be audiotaped and transcribed for formal qualitative analysis utilizing thematic analyses. Transcriptions will occur within four days of the focus group and research nurse notes will be included in these transcriptions about the content. We expect to host approximately 3-4 focus groups.

Data Analysis: Survey results will be analyzed through analytical techniques. Continuous variables will be reported as mean and standard deviation (SD) or median and inter-quartile range (IQR). Pertinent outcome variables are expected to be dichotomous. (e.g., tobacco use, gender, alternative medicine use).

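### The KAP survey's reliability is to be reported only from a pilot of fewer than 20 people; the enrolled patients would give a far more precise figure from data already being collected

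*Combined protocol and SAP*

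**What the plan says.** Under Instruments/Procedures, KAP (Specific Objective 1), the survey is assembled by adapting questions from existing cardiovascular KAP surveys. On the pilot the text reads: "The survey will piloted on a small sample (N<20) of persons (who will be excluded from the final study"). Two purposes are given. One is quantitative, "in order to report upon the internal consistency or reliability of the survey in Kiswahili"; the other concerns content, "and to assess the content validity of the survey in Kiswahili". The step to the main study is: "After acceptability is assured the survey will then be given to all patients enrolled in the study".

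Under Study Population: "We plan to enroll 500 patients in the observational study of patients with ACS-related symptoms and 500 patients in the ACS prevalence study". Under Survey Data Collection, the surveys are given verbally: "They will be administered by healthcare providers in the standard medical language of English or Swahili".

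The Data Analysis paragraph says "Survey results will be analyzed through analytical techniques". It then gives means with SD or medians with IQR for continuous variables, and adds "Pertinent outcome variables are expected to be dichotomous". It contains no reliability analysis of the main-study surveys. Nothing in the documents rules one out.

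**The concern.** The Study Design paragraph makes the KAP survey the source of the quantitative data on knowledge of acute coronary syndrome and barriers to care. The instrument is newly put together, used in Kiswahili and read aloud, so a reader of the Objective 1 results will want to know how reliable it is in this setting.

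As written, the only answer comes from at most 19 people. A sample that small can serve content validity, wording and comprehension. It is a poor basis for a numerical reliability coefficient, whose interval will be wide. Meanwhile several hundred patients will complete the survey, and the plan does not use their answers for this purpose. What is at stake is how precisely a supporting property of the Objective 1 instrument is known.

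**Working it through.** **The plan's own figure.** The limit of fewer than 20 has no calculation behind it to reproduce. No target reliability, interval width, confidence level or item count is given.

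**Inputs from the documents**
- Pilot size: 19 at most (KAP section).
- Main study: 500 per cohort, up to 1000 in all (Study Population). The calculation uses 500 as the main comparison because some surveys may be in English.

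**Assumptions (not in the documents)**
- Coefficient: Cronbach's alpha, observed value 0.70, varied from 0.60 to 0.90.
- Number of items k: 10, varied from 5 to 30.

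**Formula.** Feldt's F-based 95% interval for an observed alpha a, with n people and k items, takes F quantiles on (n − 1) and (n − 1)(k − 1) degrees of freedom:

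- lower limit = 1 − (1 − a) × F(0.975)
- upper limit = 1 − (1 − a) × F(0.025)

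**Results for a = 0.70, k = 10**

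| n | df | F(0.975) | F(0.025) | Lower limit | Upper limit | Width |
|---|---|---|---|---|---|---|
| 10 | 9, 81 | 2.275 | 0.292 | 1 − 0.30 × 2.275 = 0.32 | 1 − 0.30 × 0.292 = 0.91 | 0.59 |
| 19 | 18, 162 | 1.836 | 0.447 | 1 − 0.30 × 1.836 = 0.45 | 1 − 0.30 × 0.447 = 0.87 | 0.42 |
| 500 | 499, 4491 | 1.136 | 0.874 | 1 − 0.30 × 1.136 = 0.66 | 1 − 0.30 × 0.874 = 0.74 | 0.08 |
| 1000 | 999, 8991 | 1.095 | 0.910 | 1 − 0.30 × 1.095 = 0.67 | 1 − 0.30 × 0.910 = 0.73 | 0.06 |

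Before rounding, the widths at 19 and 500 are 0.417 and 0.079. The ratio is 0.417 / 0.079 ≈ 5.3, so the pilot interval is about five times wider than that from one cohort.

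**Sensitivity to the item count (a = 0.70).** For 5 to 30 items, the lower limit at n = 19 runs from 0.42 to 0.47 and the upper limit stays at 0.86 to 0.87. At n = 500 the interval remains 0.66 to 0.74.

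**Sensitivity to the observed alpha (k = 10)**

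| Observed alpha | n = 19 | n = 500 |
|---|---|---|
| 0.60 | 0.27 to 0.82 | 0.55 to 0.65 |
| 0.70 | 0.45 to 0.87 | 0.66 to 0.74 |
| 0.80 | 0.63 to 0.91 | 0.77 to 0.83 |
| 0.90 | 0.82 to 0.96 | 0.89 to 0.91 |

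**Other forms of reliability.** The protocol speaks of internal consistency or reliability, so two cross-checks were made.
- Test-retest correlation of 0.70, Fisher z interval: atanh(0.70) ± 1.96/√(n − 3). At n = 19 this is 0.867 ± 0.490, or 0.36 to 0.88 after back-transformation. At n = 500 it is 0.867 ± 0.088, or 0.65 to 0.74.
- Simulated alpha with 10 dichotomous items and a true value of about 0.70: the central 95% of estimates is 0.35 to 0.83 at n = 19 and 0.66 to 0.73 at n = 500.

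The imprecision does not depend on the choice of coefficient.

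**The case against.** A reader might infer three stronger points. The documents do not support them.

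- **That reliability is a gate which could pass a poor survey or fail a good one.** The only condition for going ahead is acceptability. No coefficient or cut-off is named, so any pass/fail error rate would depend on a threshold the reader supplied.
- **That a pilot of 19 tells one nothing.** It is imprecise, but a clearly poor scale would usually show. With 10 items, a scale whose true alpha is 0.50 gives an estimate of 0.70 or more in only 5% of such pilots (0.70 is used here purely for illustration). An observed 0.90 would still be fairly well bounded, at 0.82 to 0.96.
- **That leaving pilot participants out of the final study is a fault.** It is normal practice for a draft instrument tested before recruitment.

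The strongest remaining objection is that internal consistency concerns items combined into a scale, and the plan defines no KAP score. The Data Analysis examples are single yes/no variables, for which alpha has little bearing. The survey itself is not in the text available for review, so its items, subscales and scoring are unknown. This stands, and it limits the point to any multi-item scale that is actually scored. It does not remove the point, because the protocol itself undertakes to report internal consistency or reliability.

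It is also fair to say that confining the pilot to wording and content would lose the only check before fielding. That stands, and the pilot check should be kept.

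**Conclusion.** The point holds as a minor, optional improvement. The protocol names a pilot of fewer than 20 as the source of the survey's reported reliability and plans no estimate from the patients who will complete it. With an assumed alpha of 0.70 and 10 items, the pilot at its largest would leave alpha anywhere from about 0.45 to 0.87, against 0.66 to 0.74 from one cohort of 500. The contrast holds for 5 to 30 items and for a test-retest correlation. It matters less in practice if reliability is near 0.9.

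The conclusion rests on the assumed coefficient and item counts, and on at least one KAP scale being scored. The Kiswahili count may fall somewhat below 500 per cohort if some patients answer in English. The prevalence estimates, including the broad objective, and proportions from single survey items are not affected.

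**What to change.** Keep the pilot for wording, comprehension, content validity and a preliminary reliability check, labelled as preliminary. Then:

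- In the KAP section, name any multi-item scale that will be scored.
- In Data Analysis, state that for each such scale the reported internal consistency (alpha or omega with a 95% confidence interval, and item-total correlations) will be estimated from the enrolled patients' Kiswahili surveys, by cohort and pooled.
- If no scale is to be scored, say so; internal consistency then need not be reported from the main sample.

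The cost is a sentence or two in the plan and a few lines of analysis on data already being collected, with no extra participants or visits. The small downside is timing: the main-sample estimate comes after the survey has been fielded, so it can qualify the interpretation of a weak scale but cannot prevent its use.

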Physician beliefs and practices may also be contributing to under-diagnosis of ACS. If physicians do not consider the diagnosis of ACS or do not pursue diagnostic workups (such as ECGs) for patients with symptoms suggestive of ACS, their behavior may be reinforcing a misperception that ACS is a relatively uncommon and unimportant disease in the region. Studies performed elsewhere in sub-Saharan Africa have shown that physician beliefs and practices contribute to misdiagnosis and inappropriate treatment for infectious syndromes ⁸. The degree to which physician practices may be similarly contributing to under-appreciation of ACS in Tanzania is unknown.

Statement of the Problem:

Little is known about the prevalence of ACS in sub-Saharan Africa or the ways in which patient and physician practices may be affecting detection of this disease.

Rationale:

This project will gather information in order to determine the prevalence of ACS in emergency department in Moshi, Tanzania. Patient and physician perceptions and practices which may be contributing to ACS under-diagnosis will also be explored.

Broad Objective:

To determine the prevalence of ACS among adults in the emergency department.

Specific Objectives:

Specific Objective 1: To explore the knowledge, attitudes, and practices (KAP) of community members and physicians regarding ACS and ACS-related symptoms in northern Tanzania.

Specific Objective 2: To determine the prevalence of ACS-related symptoms in an emergency department in northern Tanzania and describe current patterns of care for such patients.

Specific Objective 3: To determine the prevalence of acute myocardial infarction in an ED population in northern Tanzania.

Methods:

Setting: Moshi is located in the Kilimanjaro region of Northern Tanzania. It has a population of 184, 292 people and includes both Moshi Rural and Moshi Urban. It is home to Kilimanjaro Christian Medical Center (KCMC) which is a referral hospital for northwestern Tanzania and a regional training center. Duke and KCMC have developed a research infrastructure with proven success in NIH funded grants. Many successful research projects have been conducted through the Casualty department with the help of an experienced team of Tanzanian research nurses and data entry technicians.

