Retrospective Chart Review (Specific Objective 2): Patient logs from the Emergency Department for a six-month period prior to study initiation date will be reviewed. From these logs, data will be collected including patient age, sex, and diagnosis. No identifying information such as name or date of birth will be collected. This data will allow for an analysis of current patterns of ACS-related diagnoses in the ED.

Prospective observational study of patients with ACS-related symptoms (Specific Objective 2): A triage system in the KCMC ED is about to be implemented to improve quality of care. The triage nurse, as part of routine care, will begin obtaining all five vital signs (blood pressure, heart rate, temperature, respiratory rate, and oxygen saturation). Patient complaints will be entered into a triage registry, along with patient age, sex, and vital signs. This registry data will be collected for our research purposes. No identifying information will be entered into this registry or our data collection. This triage registry will act as a quality improvement initiative to evaluate the triage process in the ED. As this registry will become part of routine care as a quality improvement project for the ED, patients will not undergo informed consent to have their vital signs and chief complaints in the triage registry. The de-identified data from this registry will be used to determine the prevalence of ACS-related chief complaints such as chest pain and shortness of breath among emergency department patients. This registry will be screened and patients presenting with a primary or secondary complaint of chest pain or shortness of breath will be enrolled for this prospective observational study. The ACS Patient survey (attached below) will be administered to all participants. Patients will be followed through their emergency department stay; their diagnostic workup, treatment, diagnosis, and disposition will be observed and recorded.

ACS prevalence study (Specific Objective 3): Following the observational study, all adult patients presenting to the KCMC Emergency Department with a primary or secondary complaint of chest pain or shortness of breath will be prospectively enrolled in the prevalence study. At time of enrollment, these patients will undergo testing with ECG and point-of-care troponin level, and a second point-of-care troponin level will be obtained two hours later. The results of

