This project was based on the local needs, available resources and standard practices in the KCMC Emergency Department. We have sought out collaborators both at Duke as well as at KCMC and have adapted our project to their suggestions and experiences. We will employ and train, [name], a Masters student in sociology at the Open University of Tanzania, who has considerable experience performing focus groups with the Duke-KCMC research collaboration. He will oversee both the focus groups and the administration of the KAP survey. We will continue to recruit junior faculty at KCMC to assist with all research concerns and plan to collaborate with [name], nephrologist and chair of the internal medicine department at KCMC for future publications and research project.

Subject Recruitment and Compensation:

All patients at KCMC Casualty Department who meet inclusion criteria will be offered enrollment in the study. The only cost to participants is the time spent performing the survey. The participants will not be compensated for their time for this study. Participants will not be compensated for their time spent completing the survey. They will be compensated for travel and food if they return for focus groups.

Consent Process:

For patients we will be utilizing a written informed consent. Participants will be provided with a description of the study objectives and procedures, along with information on data safety. Agreement to participate in the survey will serve as consent to participate in the study. The in-depth interviews will have an implied consent language. The participants will be enrolled by study nurses.

Dissemination and Publications:

Dissemination of results will occur for both the academic literature in the form of international presentations and research manuscripts as well as the clinical environment at KCMC. We will offer to KCMC leadership to discuss our results during the weekly Clinical Case Conference in order to educate KCMC Clinicians. Similarly, presentations in the Casualty Department will take place for KCMC Casualty Department staff and all healthcare providers. We also hope to share these results with emergency department providers and health policy officials in order to understand the burden of disease suffered by our patients in hopes of planning for the needs of healthcare professionals for these patients.

Budget:

Item	Cost in US Dollars
RN time x 12 months	9,600
RN data/internet time x 8 months	500

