Printing .13 x sheet	3328
Automatic BP cuff x 2	100
Alcohol pads (1/per subject)	donated
POC troponin machines	donated
EKG paper	donated
ECG machines	donated
Patient focus group transportation/food/time x 100 subjects	300
MD indepth interview food x 3	100
KCMC overhead 10% total budget	3213
Total	15,321

Budget Justification:**PERSONNEL**

Research nurse: One full time research nurse will be required for all the aims of this study.

They will be employed according to the research project requirements and will be active on other projects thus supplementing their salary during periods when less participant contact is needed.

The research nurses will be responsible for recruiting patients for the surveys, follow-up groups and performing blood pressure measurements, ECGs, and troponins. They will also be responsible for informed consent of participants, conducting all interviews, maintaining participant files, and communicating progress to [name]. Nurses will be paid \$800 per month, which is standard for Duke/KCMC Collaboration research nurses. One nurse will be full-time for 12 months (\$9,600).

SUPPLIES:

Laboratory equipment: One alcohol pad will be required for each patient and these supplies will be donated.

Two automatic blood pressure cuffs will be needed. (\$100) ECG machines, POC troponin machines, and cartridges will be donated.

Paper and printing costs: (\$3,328) We request funds in order to cover paper and printing costs for the project. Informed consent, surveys and any regulatory paperwork will need printing estimating 16 pages/participant x 1600 participants at 25,600 pages at 0.13 cents for paper and printing costs. Total funds requested \$3,328.

Patient focus group transportation and food: Ten focus group will be held x 10 patients each. Each participant will be reimbursed (5,000 TSH)= (\$3USD) for transportation plus food.(\$300)

In-depth interview: Interviewee will be paid for their time and provided with a meal. (\$100)

KCMC overhead According to our funders, the US National Institute of Health guidelines, we are requesting 10% of the total KCMC budget be paid to the Good Samaritan Foundation account at KCMC hospital for the privilege of being housed at KCMC and other administrative costs.

References

1. WHO | A global brief on hypertension. *WHO*. 2013.

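### The prevalence study claims all symptomatic adults in one place and a representative sample in another, but its accrual and staffing support only part of the week, and no listed field would show who was missed

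*Combined protocol and SAP*

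**What the plan says.** Four statements in the combined protocol and SAP set the population:

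- Specific Objective 3: "To determine the prevalence of acute myocardial infarction in an ED population in northern Tanzania".
- ACS prevalence study: enrolment takes in "all adult patients presenting to the KCMC Emergency Department with a primary or secondary complaint of chest pain" or shortness of breath.
- Subject Recruitment and Compensation: "All patients at KCMC Casualty Department who meet inclusion criteria will be offered enrollment in the study".
- Study Design: a "cross-sectional survey of a representative sample of all casualty department patients presenting with chest pain or shortness of breath", with no method given for drawing the sample.

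None of the four is limited by hour or day. Two further statements set the means:

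- Sample Size Calculation: "given current patient volumes at KCMC (25 adults/dayshift), enrollment will need to be conducted for 5 months to achieve the desired sample size".
- Budget Justification, Personnel: "One full time research nurse will be required for all the aims of this study". The cost is $800 a month for 12 months, $9,600 in all.

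The triage registry, described under the prospective observational study, is listed as holding complaint, age, sex and vital signs. The document does not state enrolment hours, night or weekend cover, a log of eligible patients missed, or a comparison of enrolled with other eligible patients.

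**The concern.** A prevalence is defined by its denominator. If recruitment happens only while a research nurse is on duty, arrival time becomes an unwritten eligibility criterion, separate from the written exclusions for unstable or critical illness. People who arrive in the evening, at night or at weekends may differ in acuity and case mix, and a larger sample from the same hours does not reduce the resulting error.

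Two results are at stake: the prevalence of infarction, and the part of Objective 2 that follows enrolled patients through work-up, treatment and disposition. Both would be labelled as describing the whole department. Without arrival times, nobody could tell afterwards which hours they describe.

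**Working it through.** **1. The frame.** Enrolling everyone and enrolling a representative sample are different designs. The first needs cover at all hours; the second needs a sampling scheme. The document provides for neither.

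**2. Accrual, starting from the plan's own figure.** Inputs, all from Sample Size Calculation: 25 adults per day shift, 10% eligible, target 210, stated duration 5 months.

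- Eligible per day shift: 25 × 0.10 = 2.5.
- Shifts for 210: 210 / 2.5 = 84. That is 84 / 30.44 = 2.8 months at seven days a week, or 84 / 21.74 = 3.9 months on weekdays.
- The stated 5 months is not reproduced. Five months hold 5 × 30.44 × 2.5 = 380 eligible patients (seven days) or 5 × 21.74 × 2.5 = 272 (weekdays). The figure fits 210 only with an unstated capture rate of 210 / 380 = 55% or 210 / 272 = 77%.
- The calculation therefore reaches its target, with slack, without any off-shift arrival.
- For the planned 500 in the prevalence study: 500 / 2.5 = 200 shifts, 6.6 or 9.2 months. For 500 + 500 in sequence: 1,000 / 2.5 = 400 shifts, 13.1 or 18.4 months, against the 12 months of data collection in Study Timeline.

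**3. Staffing.** $9,600 / $800 = 12 nurse-months, which is one person for the year. Weekly hours are not given; 40 to 48 is assumed.

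- Share of the week covered: 40 / 168 = 24% to 48 / 168 = 29%.
- Nurses needed for continuous cover: 168 / 48 = 3.5 to 168 / 40 = 4.2.
- Day-shift cover on all seven days, with an assumed shift of 8 to 12 hours, takes 7 × 8 = 56 to 7 × 12 = 84 hours. That also exceeds one nurse.

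**4. Whether the gap could be checked later.** The registry could serve as the denominator of symptomatic adults, but its listed fields include no arrival date or time. Presenters and enrolled patients could not be set side by side by shift.

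**5. Bias.** Let s be the share of symptomatic adults arriving in uncovered hours, and p1 and p0 the prevalence in covered and uncovered hours. The error from reporting p1 for the whole department is

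p1 − [(1 − s)p1 + s·p0] = s(p1 − p0).

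The document gives neither s nor prevalence by hour. Take p1 = 10%, and assume s of 20% to 65% and p0/p1 of 0.5 to 2. The extremes are 0.65 × (10 − 20) = −6.5 points and 0.65 × (10 − 5) = +3.25 points, with zero when p0 = p1. This range is not an estimate. It shows that even the sign is open.

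**The case against.** The best reply is that an unstated schedule is not a restricted one. No section gives enrolment hours or excludes off-shift arrivals. The day-shift volume appears only in an accrual estimate, and that estimate does not fit the 500 + 500 targets. Its 10% is a figure for chest pain, although shortness of breath also qualifies, so it is weak evidence of the roster. Other text points to more hands: study nurses in Consent Process, research nurses in the plural in Budget Justification, a seasoned research team in Setting, and healthcare providers giving the surveys in Survey Data Collection.

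Much of this stands. A reader might infer that the study yields a day-shift prevalence, or that an off-shift patient is never approached; the document does not establish either. The mismatch remains, however. The plural wording adds no funded time and no roster, and the budget text says the nurse will also work on other projects when contact is low.

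Three further inferences also go too far:

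- *That the bias rivals the sampling error.* With a 50% off-shift share and off-shift prevalence of 6% to 15% against 10%, the whole-department figure is 8.0% to 12.5%. That is up to 2.5 points away, next to a 95% half-width of 2.6 at n = 500. Every input is assumed. At a 30% share the largest error is 0.3 × 5 = 1.5 points, and the plan's own stated precision is ±5 points.
- *That out-of-hours care goes unobserved.* The six-month log review and the triage registry are not described as limited by hour. They do not record work-up, but they serve part of Objective 2.
- *That late-shift patients lose the two-hour troponin.* The last two hours are 2/8 = 25% or 2/12 = 17% of an assumed shift, but shift length, arrival pattern and handover are all unstated. This is a possible consequence only.

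**Conclusion.** The concern holds in a limited form. The document contradicts itself on who is sampled, and as resourced it would probably miss many off-shift arrivals under either description. That conclusion rests on the 12 funded nurse-months, on the day-shift accrual figure, and on an assumed working week of 40 to 48 hours (24% to 29% of all hours). It does not depend on whether 210 is the right sample size.

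The effect on the prevalence estimate is unknown in size and direction and may be nil. The firm defect is that the plan would describe a probably partial-hours sample as the emergency department, while its listed fields could not show whether that matters.

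**What to change.** 1. Replace the two descriptions with one frame: adults with the qualifying complaints who present during staffed enrolment hours, or who are still in the department when those hours begin. State the hours and days.
2. Add arrival date and time to the triage registry and to the enrolment record. Tabulate all symptomatic adults against enrolled patients by shift and weekday, with age, sex, complaint and vital signs. The comparison is of totals, so it needs no linkage of individuals.
3. Report patients held over from the night separately, since those still present in the morning are a selected group. State the main prevalence as applying to the hours actually covered, and extend it to the whole department only with the table from item 2 alongside.

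Reweighting to the registry's shift distribution is not a substitute: a shift with no enrolled patients has nobody to weight.

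The cost is one extra registry field, also entered in the enrolment record, a rewritten enrolment sentence and one table, with no added staff. The price is a narrower stated conclusion.
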